6.4.5 Analysis of MRI Endpoints

The following MRI endpoints will be analyzed:

- Lesion parameters:
 - o number of Gd-enhancing lesions;
 - o number of new or newly-enlarging T2 lesions; and
 - o number of new T1 hypointense lesions.
- Volume parameters:
 - o volume of Gd-enhancing lesions;
 - o volume of T2 hyperintense lesions; and
 - o volume of T1 hypointense lesions.
- Other parameters:
 - o brain atrophy (percent brain volume change [PBVC]); and
 - o magnetization transfer ratio (MTR).

MRI endpoints will be summarized using the following analysis populations, treatment grouping, and datasets:

 Study 109MS303 MRI Cohort with Combined Treatment Grouping and Combined Data

The number of Gd-enhancing lesions will be descriptively summarized, both overall and over time, by treatment group, both as a continuous variable and categorically.

The number of new or newly-enlarging T2 lesions will be descriptively summarized, both overall and by key time intervals, by treatment group, both as a continuous variable and categorically. The negative binomial regression model will be used to estimate adjusted means and 95% confidence intervals for each treatment group. The model will adjust for region and baseline volume based on the Previous Study Baseline.

Examples of key time intervals may include, but are not limited to: Previous Study Baseline to Week 24 in Previous Study, Week 24 to Week 48 in Previous Study, Week 48 to Week 96 in Previous Study, Week 96 of Previous Study to Week 48 of Study 109MS303, Week 48 of Study 109MS303 to Week 96 of Study 109MS303, and up to Week 336 of Study 109MS303 to Week 384 of Study 109MS303, Previous Study Baseline to Week 48 of Previous Study, Previous Study Baseline to Week 48 of Study 109MS303, and up to Previous Study Baseline to Week 384.

The number of new T1 hypointense lesions will be analyzed in a similar manner as the number of new or newly-enlarging T2 lesions.

The actual value of MRI volume parameters, as well as the change and percentage change in these parameters for key time intervals (similar to those used for analysis of T2 lesions), will be descriptively summarized by treatment group.

Brain atrophy (PBVC) and MTR will also be descriptively summarized by treatment group for key timepoints and time intervals.

Analyses utilizing the Studies 109MS301 + 109MS302 MRI Cohort will descriptively present the number of new lesions, as well as change in lesion volume for key time intervals (e.g., Previous Study Baseline to Week 48 in Previous Study, Week 48 to Week 96 in Previous Study, Week 96 in Previous Study to Week 48 in Study 109MS303, Week 48 in Study 109MS303 to Week 96 in Study 109MS303 to Week 96 in Study 109MS303 to Week 144 in Study 109MS303, Week 144 in Study 109MS303 to Week 192 in Study 109MS303, and up to Week 336 in Study 109MS303 to Week 384 in Study 109MS303).

As a result of Study 109MS303 becoming an open label extension with one single arm after regulatory approved the dosage of BG00012 240 mg BID, all patients receiving BG00012 240 mg TID were switched to BG00012 240 mg BID. Hypothesis tests of comparison between treatment groups for MRI endpoints will not be conducted.

For MRI analyses, data following first use of alternative MS medications will be excluded. Some MRI endpoints for Study 109MS303 MRI Cohort with Combined Treatment Grouping and 109MS303 Data may be analyzed.

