6.3.8 Day Ranges for Analyses by Visit

Subjects do not always strictly adhere to the visit schedule timing in protocols. Therefore, the designation of visits (or timepoints) will generally be based on the day of evaluation relative to date of first dose of study medication within a given dataset (i.e., with the date of first dose of study medication being Study Day 1), rather than the nominal visit recorded in the clinical database.

Mutually exclusive visit windows will generally be utilized to assign visits for analysis that correspond to post-baseline visits specified in the protocols. In general, for data that are summarized by visit, visits for analysis will be assigned by using a windowing scheme as described below.

Within a given dataset, the upper bound of the baseline visit window is Day 1, and the lower bound of the first post-baseline visit window is Day 2. For all other lower and upper bounds of visits, windows will end at the midpoint between scheduled visit timepoints, with the midpoint in the latter visit window.

If more than one observation occurs within the same window, data closest to the target day for the scheduled visit will be used for analysis. If more than one observation is the same distance from the target day, the last observation will be used for analysis.

However, for MRI analyses, visit windowing will only be applied when the nominal visit designation is premature withdrawal, with the lower bound of the first post-baseline visit window being Day 169 and with all other lower and upper visit bounds defined as above.

Otherwise, MRI analyses will not utilize visit windowing and will present results by nominal visit designations.

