measured by EDSS at		109MS303	Combined Treatment	109MS303 Baseline	Kaplan Meier analysis of time to the 6-month
selected time points		Data	Grouping		sustained disability progression will be used to
					estimate the proportion at selected time points.
EQ-5D: EQ5D VAS,	109MS303	Combined Data	Combined Treatment	109MS301/109MS302	Descriptive statistics by combined treatment group
EQ-5D index score and	ITT population		Grouping	Baseline	and by study visit.
EQ-5D individual					
questions					
SF-36 scores	109MS303	Combined Data	Combined Treatment	109MS301/109MS302	Descriptive statistics by combined treatment group
	ITT population		Grouping	Baseline	and by study visit.
Visual function test	109MS303	Combined Data	Combined Treatment	109MS301/109MS302	Descriptive statistics by combined treatment group
	ITT population		Grouping	Baseline	and by study visit.
MRI endpoints	109MS303	Combined Data	Combined Treatment	109MS301/109MS302	Descriptive statistics by combined treatment group
	MRI Cohort		Grouping	Baseline	and by study visit.
					For the total number of new or newly enlarging T2
					lesions, the total number of new T1 lesions, and the
					total number of Gd-enhancing lesions: negative
					binomial models may be used, adjusted for baseline
					characteristics in previous studies.

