Annualized relapse rate (ARR) will be summarized using the following analysis populations, treatment grouping, and datasets:

- Studies 109MS301/302/303 ARR, overall and over time, using the Study 303 ITT Population with Combined Treatment Grouping and Combined Data; and
- Study 109MS303 ARR using the Study 303 ITT Population with Combined Treatment Grouping and Study 109MS303 data only.

The number of subjects with a given number of relapses (categories of 0, 1, 2, 3, and 4 or more relapses), total number of relapses, and total number of subject-years of follow-up will be summarized by treatment group. The unadjusted ARR will be calculated for each treatment group as the total number of relapses divided by the total number of subject-years

of follow-up. Relapses and follow-up time that occur after first use of alternative MS medications are excluded from the calculations.

The adjusted ARR and associated 95% confidence interval will be calculated for each treatment group by using a negative binomial regression model for unadjusted ARR, adjusting for baseline EDSS score (≤2.0 vs. >2.0), baseline age (<40 vs. ≥40 years old), region, and baseline relapse rate (i.e., the number of relapses in the year prior to the date of first dose in the previous study) as covariates. The baseline definition for these covariates will be based on Previous Study Baseline.

The logarithmic transformation of the time on the study will be included in the model as the "offset" parameter. If the data are underdispersed, or if the negative binomial regression model does not converge, a Poisson regression model with the same covariates will be used instead of the negative binomial regression model. Dispersion will be evaluated from the Pearson Chi-Square statistic. If the ratio of the Pearson Chi-Square statistic to the degrees of freedom is ≤ 1 which indicates no overdispersion, then a Poisson regression model with adjustment for underdispersion will be used.

In addition, the subject relapse rate will be calculated as the number of relapses for an individual subject divided by follow-up time in years for that subject excluding follow-up time after first use of alternative MS medication. Subject relapse rate will be summarized descriptively by treatment group.

ARR analyses over time will be presented by various time intervals in order to elucidate onset and maintenance of effect over time. For example, time intervals one year in length may be considered.

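### The negative binomial models for new T2 and T1 lesion counts state no exposure term, although the scan interval behind a count can differ between subjects

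*SAP*

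**What the plan says.** For new or newly enlarging T2 lesions, SAP 6.4.5 says the counts "will be descriptively summarized, both overall and by key time intervals, by treatment group". It then says: "The negative binomial regression model will be used to estimate adjusted means and 95% confidence intervals for each treatment group". The adjustment is given in one sentence: "The model will adjust for region and baseline volume based on the Previous Study Baseline". New T1 hypointense lesions are handled in the same way. Neither an offset nor any other exposure term is named.

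The MRI row of the 6.4.2.1 table refers to totals: "For the total number of new or newly enlarging T2" lesions, and likewise total new T1 and total Gd-enhancing lesions, negative binomial models may be used, adjusted for parent-study baseline characteristics. Again there is no exposure term.

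For annualised relapse rate, SAP 6.4.3 is explicit: "The logarithmic transformation of the time on the study will be included in the model", as an offset.

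These provisions determine how long each subject is covered by scans:

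- SAP 2.3: scans are yearly in the extension and at premature withdrawal, up to Amendment 6.
- SAP 6.3.8: "visit windowing will only be applied when the nominal visit designation is premature withdrawal". The first such window opens at Day 169, and other MRI results use nominal visits.
- SAP 2.2 and Protocol 7.2.1: extension baseline may fall up to 6 months after parent Visit 24.
- SAP 6.4.5 and 6.1: MRI data after first alternative MS medication are dropped, and in general nothing is imputed.

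**The concern.** New T2 and T1 lesions accumulate between two scans, so an expected count is a rate multiplied by the time those scans span. A model for the mean count without an exposure term treats all spans as equal. If they are not, the adjusted mean mixes lesion activity with length of observation. For an overall total, the result has no defined time unit even within one group.

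The plan presents these means with 95% confidence intervals for up to six combined treatment groups, in support of a secondary objective on long-term MRI effects. Readers will compare them side by side. If one group had been scanned for less time, its lower mean could be mistaken for lower disease activity.

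**Working it through.** **1. The plan's own figure.** By the midpoint rule in SAP 6.3.8, with first extension dose on Day 1 and Week 48 on Day 7 × 48 + 1 = 337, the first window opens at (1 + 337)/2 = 169. This reproduces Day 169.

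**2. Interval length after windowing.** The Week 96 target is Day 673, so the next window opens at (337 + 673)/2 = 505 and the Week 48 window is Day 169 to Day 504. A withdrawal scan assigned to Week 48 is therefore 168 to 503 days after Day 1, against 336 nominal: a ratio of 0.50 to 1.50. Later windows up to Week 336 have the same width. Where two scans share a window, the one closer to target is kept. Ratios well above 1 thus arise mainly when the scheduled scan was missed.

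**3. Effect on one fixed interval.** Suppose fractions fA and fB of two groups use a windowed scan at length ratio r, with equal and constant lesion rates. The apparent ratio of means is (1 − fA + fA·r)/(1 − fB + fB·r). The fractions are assumptions; the documents give none.

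| fA, fB | r = 0.50 | r = 1.50 |
|---|---|---|
| 10%, 5% | 0.950/0.975 = 0.974 | 1.050/1.025 = 1.024 |
| 20%, 10% | 0.900/0.950 = 0.947 | 1.100/1.050 = 1.048 |

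**4. The parent-to-extension interval.** SAP 6.4.5 lists parent Week 96 to extension Week 48. With no delay it spans 48 weeks. With a 6-month delay (taken as 26 weeks) it spans 48 + 26 = 74 weeks, and 74/48 = 1.54. Cumulative intervals crossing the transition carry the same extra time. The documents do not say how many subjects had a delay. Baseline assessments could be repeated after a treatment gap, so some subjects may have a later starting scan.

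**5. Overall totals.** With a constant and equal rate, expected count = rate × time, so the apparent ratio is the ratio of mean scan-covered times. Assumed examples: 4.5 versus 5 years gives 0.90, 4 versus 5 gives 0.80, and 3 versus 5 gives 0.60.

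**6. Simulation check.** The assumptions were 150 subjects per group, 1 lesion per year in both groups, negative binomial dispersion 1, follow-up uniform within 2 years of its mean, and 400 runs. Coverage is the share of runs whose 95% confidence interval for the group ratio includes 1.

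| Mean years | No offset: ratio, coverage | Log-time offset: ratio, coverage |
|---|---|---|
| 5 v 5 | 0.993, 92% | 0.994, 93% |
| 4 v 5 | 0.797, 57% | 0.995, 93.5% |
| 3 v 5 | 0.597, 3% | 0.997, 95.5% |

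**7. When the rate changes.** Subjects on placebo or GA started BG00012 on entering the extension. Assume 2 lesions per year for two years, then 0.5 per year.

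| Years observed | Expected total | Ratio to 5 years, no offset | Rate per year with one offset | Ratio to 5 years, one offset |
|---|---|---|---|---|
| 5 | 4 + 1.5 = 5.5 | 1.00 | 1.10 | 1.00 |
| 4 | 4 + 1.0 = 5.0 | 0.91 | 1.25 | 1.14 |
| 3 | 4 + 0.5 = 4.5 | 0.82 | 1.50 | 1.36 |

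A single offset across the switch makes shorter follow-up look 14% to 36% worse. Fitted by period, the rates are 4/2 = 2 and 0.5 per year whatever the length of follow-up.

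**The case against.** **Silence is not exclusion.** SAP 6.4.2 says models will generally match those of the parent studies, and Section 6 omits the code. An offset could be inherited from plans not available here. The ARR rows of the 6.4.2.1 table also omit the offset that 6.4.3 states. This stands as a limit: the finding is that no offset is stated. However, the inheritance sentence covers ARR too, and there the offset was still written out. A model built for 96-week parent studies would not settle the matter for an extension scanned over many more years.

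**It is not certain that totals are modelled.** The phrase "both overall and by key time intervals" belongs to the descriptive sentence, the model sentence names no period, and the table only permits modelling of totals. This stands. The listed intervals have fixed nominal ends, and with observed data a subject lacking the end scan would ordinarily leave that interval, not enter it with a low count.

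**Stronger readings.** A reader might infer that groups losing subjects early will look better, or that windowing halves counts. The documents do not support either as a group effect. They give no MRI follow-up by group. The protocol's rationale for ending scans describes a diminished MRI cohort as a whole, and scans stopped for every group. Halving applies to a subject at the extreme lower window edge, and windowing can also lengthen an interval.

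**No test is at risk.** SAP 6.4.5 rules out between-group hypothesis tests for MRI endpoints, and the primary objective is safety. This stands and limits the consequence to description.

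**One offset over everything can mislead.** Step 7 shows this is correct for groups that switched treatment. It is a reason to fit the periods separately and does not argue against an offset within them.

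**Conclusion.** The gap is real and should be closed. As written, the models for new T2 and T1 counts carry no exposure term, while the plan's own rules allow unequal time between the scans that define a count. The proportional shift in adjusted means depends on two conditions: scan-covered time differs between groups, and lesion rates are constant. The first is not reported, so 0.80 for 4 versus 5 years illustrates the size of a possible shift and does not estimate one in this trial. Windowed withdrawal scans alone matter little in a fixed interval, about 0.95 to 1.05 under the assumed fractions. The larger exposures are any modelled totals and the intervals spanning the move into the extension. What is affected is the descriptive adjusted means and their confidence intervals.

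**What to change.** - In the interval models for new T2 and new T1 lesions, add the log of actual time between the two defining scans as an offset, and report annualised rates.
- State whether totals are modelled. If they are, fit the parent-study and extension periods separately, each with its own offset, and do not use one offset across the switch from placebo or GA to BG00012.
- Report scan-covered time by treatment group next to the adjusted estimates.
- Reconcile 6.4.5, which plans only description for Gd-enhancing lesions, with the 6.4.2.1 table, which allows a model of their total. If that total is modelled, use the log number of scans, because Gd counts belong to a scan and not to an interval.

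The cost is one model term and some period-specific output, from scan dates already recorded. The offset assumes a roughly constant rate within each fitted interval, which is easier to defend for yearly intervals than for the whole combined period.

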6.4.6 Analysis Quality of life Assessments (SF-36 and EQ-5D) and Visual Function Test

The quality of life (SF-36 and EQ-5D) and Visual Function Test assessments will be summarized using the Study 109MS303 ITT Population with Combined Treatment Grouping and Combined Data. For these analyses, data following first use of alternative MS medications will be excluded.

SF-36

Scores for SF-36 will be calculated based on the standard scoring method described in the SF-36 Health Survey Manual and Interpretation Guide. This method indicates that for an individual domain where 50% or more of the item's questions are non-missing, the average of the non-missing items for that patient in that domain will be calculated, and this average is then used to impute the missing item questions response and calculate the domain score. The mental and physical component summary measures (MCS and PCS, respectively) are then calculated from the imputed domains scores.

Actual scores and change from Previous Study Baseline over time will be descriptively summarized by treatment group for the individual domains and MCS and PCS measures.

EQ-5D

The Euroqol (EQ)-5D is a generic health-related quality of life instrument which has been extensively validated. There are two components to the EQ-5D, a Health State Profile that results in calculation of an EQ-5D index score and a Visual Analog Scale (VAS) that results in calculation of the subject assessment of health scale.

For the Health State Profile, patients record their level of current health for five domains comprising a health profile: mobility, self-care, usual activities, pain/discomfort, and anxiety/depression. Scores of 1, 2, or 3 are possible responses for each of the five questions in the Health State Profile (1=no problems, 2=some problems, 3=severe problems). The digits for the five dimensions are combined in a 5-digit number describing a person's health state. A scoring formula developed by the EuroQol Group is then used to assign utility values for each patient's Health State Profile. A summary index score (EQ-5D index score) is derived from the 5 questions by conversion with this scoring formula and a table of scores.

For the VAS, patients are asked to rate their current health on a 20 cm scale from 0 to 100 where 0 represents "worst imaginable health state" and 100 represents "best imaginable health state" resulting in the subject assessment of health scale.

Actual scores and change from Previous Study Baseline over time will be descriptively summarized by treatment group for both the EQ-5D index score and subject assessment of health scale. Additionally, the scores for each of the five component questions of the EQ-5D index score will be summarized categorically.

Visual Function Test

The visual function test uses the low-contrast Sloan letter chart as an indicator of disease-related changes in visual performance. Subjects are tested using the contrast level of 100%, 2.5% and 1.25% charts, and the scores are defined as the number of letters identified correctly for each chart (maximum score is 60).

Actual scores and change from Previous Study Baseline over time will be descriptively summarized by treatment group for the VFT for each of the contrast levels.

6.5 Safety Data

6.5.1 Analysis Population

Analysis populations, treatment groupings, and datasets are detailed in Section 6.2 above.

Study 109MS303 Safety Population is defined to include all subjects who received at least one dose of study treatment in Study 109MS303 and had any post-baseline safety follow-up in Study 109MS303, defined as any treatment emergent AE in Study 109MS303 or any post-baseline laboratory, vital signs, or physical exam assessment in Study 109MS303. This definition of the safety population is utilized in order not to inflate the denominator for calculation of incidences and percentages (and therefore deflate the incidences and percentages themselves) with subjects who were dosed in Study 109MS303 but had no post-baseline safety follow-up.

The analysis populations, treatment groupings, and datasets for safety analyses will be as follows:

- Primary safety analyses will utilize the Study 109MS303 Safety Population with Combined Treatment Grouping and Study 109MS303 data only; and
- Select safety analyses (where the incidence in Study 109MS303 itself may be of interest) will utilize the Study 109MS303 Safety Population with Study 109MS303 Treatment Grouping and Study 109MS303 data only.

6.5.2 Analysis Methods

Safety analyses will summarize adverse events (AEs), laboratory abnormalities, and vital signs.

6.5.3 Analysis of Adverse Events

All summary analyses of AEs will be based on the principle of treatment emergence. In a given dataset, an event is considered to be treatment emergent if it has an onset date on or after the date of first study treatment or if it was present prior to start of study treatment and subsequently worsened. Henceforth, whenever an analysis or summary of AEs is mentioned, it is intended that this is in reference to the treatment emergent adverse event experience, even if not explicitly mentioned.

In general, analyses of AEs will include all events through the end of a subject's follow-up in a given dataset.

In general, AEs will be analyzed based on *incidence*, defined as the proportion of subjects who had at least one occurrence of an event out of the number of subjects in the relevant safety analysis population.

The Medical Dictionary for Regulatory Activities (MedDRA) version 13.1 will be utilized to code and group AEs by System Organ Class (SOC) and Preferred Term (PT). References to summaries of AEs using System Organ Class are intended to refer to the primary SOC. In addition to summaries of incidence by both SOC and PT, incidence of adverse events may also be summarized and presented by SOC only or by PT only, as appropriate, depending on the nature of the analysis performed. Adverse event summaries may also be provided by

High-Level Group Term (HLGT) or High-Level Term (HLT), if considered appropriate for signal detection, in instances where the SOC level of summary is too broad but the PT level of summary is too granular.

A summary analysis of adverse events will be provided including the following numbers and incidences/percentages of subjects: in the safety analysis population; with an adverse event; with a moderate or severe AE; with a severe AE; with a related AE; with a serious adverse event (SAE); with an AE leading to discontinuation of study treatment; and with an AE leading to withdrawal from study.

Summaries of the most frequently reported AEs by PT will also be presented, defined as those AEs with an incidence of AEs of at least 5% (at SOC or PT level) in any treatment group. Other cutoff values may be explored, as appropriate.

The incidence of AEs by SOC and PT may also be presented by time intervals (e.g., using a 12 month time interval). Other time intervals may be explored as well to elucidate trends over time. For such analyses, for a given time interval, the number of subjects who were followed for adverse events during that time interval will be presented along with the AE incidence during that time interval. Therefore, for a given SOC or PT, subjects will be counted only once for a given time interval but may be counted more than once across time intervals.

The incidence of AEs by relationship to study treatment will be summarized by SOC and PT. For a given SOC or PT, subjects with multiple AEs differing in relatedness will be counted once in the most related category. In addition, AEs categorized as "related" (i.e., those where the investigator assessment of relationship to study treatment is "possibly" or "related) will also be summarized by PT.

The incidence of AEs by severity will be summarized by SOC and PT using severity categories of mild, moderate, and severe. For a given SOC or PT, subjects with multiple AEs differing in severity will be counted once in the category of worst severity. The incidence of severe AEs will also be summarized by PT.

Deaths that occur will be described in detail in patient narratives. A listing of deaths will also be provided. While the number of deaths is expected to be small, tabulation will be performed if appropriate.

A summary of SAEs by SOC and PT will also be provided. Details of each SAE will also be listed, including subject ID, treatment group, system organ class/preferred term, date of onset, severity, and relationship to the study drug and action taken. In addition, a summary of treatment-related SAEs by SOC and PT will be provided.

The incidence of adverse events that led to study treatment discontinuation, study withdrawal, dose interruption, and dose reduction will each be presented by SOC and PT.

A listing of AEs leading to study treatment discontinuation and study withdrawal will also be presented. Adverse events that were treatment-emergent to the previous study yet led to study treatment discontinuation and study withdrawal in Study 109MS303 will be denoted by a negative onset day in the listing.

The incidence of adverse events of special interest will be summarized by SOC and PT. The adverse event of special interest categories may include the following:

- Flushing and other related symptoms;
- Gastrointestinal tolerability;
- Infections, including potential opportunistic infections;
- Ischaemic cardiovascular disorders;
- Hepatic disorders;
- Renal disorders;
- Malignancies;
- Lymphopenia and Leukopenia.

Subjects who discontinue study treatment are to have a premature study withdrawal visit within four weeks of the last dose of study treatment dose and a telephone follow-up 12 weeks after the last dose of study treatment. For subjects who have discontinued study treatment, a separate summary of adverse events with onset after discontinuation of study treatment may be presented.

Subject narratives will be provided for the following event types in Study 109MS303:

- Deaths:
- Serious adverse events (only selected SAEs may be included);
- AEs leading to study drug discontinuation;
- AEs leading to study withdrawal;
- Special interest AE categories of potential opportunistic infections, ischaemic cardiovascular disorders, hepatic disorders, and malignancies;
- ALT or AST values >5xULN at any time post-baseline; and
- ALT or AST values $\ge 3xULN$ and concurrently total bilirubin values $\ge 2xULN$.

Select AE analyses utilizing the Study 109MS303 Safety Population with Study 109MS303 Treatment Grouping and Study 109MS303 data only, mentioned in the second bullet in Section 6.5.1 above, may include, but are not limited to: summary analysis of adverse events (AEs), incidence of AEs by SOC and PT, incidence of most common AEs, incidence of treatment-related AEs, incidence of severe AEs, incidence of serious adverse events (SAEs), incidence of treatment-related SAEs, incidence of AEs that led to discontinuation of study drug, incidence of AEs that led to study withdrawal, and incidence of AEs of special interest such as malignancies, hepatic disorders, GI, opportunistic infections, herpes zoster, etc.

